Title:

Comparison of placement of double-lumen endobronchial tube using Glide Scope with 2 different stylet configurations vs standard Macintosh laryngoscopy.

Principal Investigator:[name], Emory University School of Medicine

V. 03April2015

NCT02495259

Title: Comparison of placement of double-lumen endobronchial tube using GlideScope with 2 different stylet configurations vs standard Macintosh laryngoscopy.

Principal Investigator: [name]
Emory University School of Medicine
Department of Anesthesiology

Site: Emory University Hospital (EUH) and Emory University Hospital – Midtown (EUHM)

IRB: Emory University School of Medicine

Purpose of Study

To evaluate the technique of placement of the double-lumen endobronchial tube (DLT) using an included stylet that has been radically bent (ZU-bend) as compared to a commercial GlideRite stylet with the GlideScope and direct laryngoscopy using Macintosh laryngoscope.

Introduction

Placement of the DLT is viewed as more challenging partly due to bulkiness and a lack of flexibility that the DLT has compared to single lumen endotracheal tubes, as well as a larger and more fragile occlusion balloon that is more prone to rupture. Securing an airway using traditional laryngoscopy as well as video-assisted indirect laryngoscopy each has its unique advantages and disadvantages.

In a recent study comparing laryngoscopy with Macintosh blade and GlideScope the former was concluded to be superior with respect to intubation success (1), while an earlier study indicated GlideScope to be equivalent to direct laryngoscopy (4). A follow-up editorial pointed out that in Russel's study there was no inclusion of the GlideRite stylet designed specifically for use with GlideScope and DLT, possibly explaining difficulties with GlideScope-assisted intubations (2, 3).

In a small anecdotal sample, the use of a radically curved DLT stylet, the ZU-bend, and GlideScope appeared to be useful in placement of the DLTs by multiple anesthetists under supervision of one anesthesiologist ([name], presented at Thoracic Anesthesia Symposium 2015).

Therefore, we propose to merge the study protocol similar to Russel et. al. (1) with inclusion of both the suggestions from Bussier's editorial , as well as the experience with radically bent DLT stylet (ZU-bend) to evaluate each method with respect to intubation ease and to compare the complication rate with each technique.

Investigational Devices

The intubation modalities (GlideScope, Macintosh laryngoscope, GlideRite stylet and DLT intubating stylet) have all been approved for clinical use and have been used routinely at our institution for DLT placement.

Macintosh blade is one of the most commonly used direct laryngoscopy blades for both single and double-lumen endotracheal intubations. It allows the practitioner to visualize larynx for subsequent intubation.

The **GlideScope** is a video laryngoscope that provides a real-time view of the airway and tube-placement during intubation in place of the direct laryngoscope.

The **GlideRite Rigid stylet** is specifically designed to work with the GlideScope video laryngoscope to facilitate intubation. It provides necessary rigidity and curvature to an otherwise flexible endotracheal tube to permit easier manipulation of it for tracheal intubation.

ZU-bend is a specific shaping technique of the intubating stylet that is more closely related to GlideScope blade curvature. There is a commonplace practice of shaping a flexible stylet for intubation to suit a particular combination of patient and equipment variables. The degree of shaping is somewhat specific to each provider, and is a normal procedure for using the intubating stylet. Bending of the stylet prior to intubation constitutes a routine preparation step for the majority of intubations. The steps for shaping of the stylet are provided in the appendix A.

Objectives

The current research does not provide clear support for one method or another in DLT placement techniques. Additionally, our research has shown that the ZU-bend stylet may be useful with the GlideScope. This randomized controlled study will compare the efficacy of three different methods of DLT placement.

The primary outcome measures will be the mean time it takes to place a DLT with each modality. Secondary outcome measures include success rate of first endobronchial intubation attempt; assessment of difficulty by the provider and complication incidence.

The end points of evaluation of each technique were selected based on Russel's protocol with our modification as summarized in Table 1:

Table 1.

Metric:	Defined as:
First intubation attempt success	DLT placed during initial laryngoscopy, within 120s
Duration of laryngoscopy	Time from laryngoscope at pt's lips through 1 st EtCO ₂ detection
Blood on device	Yes/No
SpO ₂ <96% during intubation	Yes/no
Voice changes	Evaluated in PACU - subjective answer by patient
Lip trauma	Evaluated immediately post-intubation
Dental trauma	--/--
Sore throat	Analog pain scale 0-10, subjective answer in PACU
DLT cuff rupture	Loss of air pressure during procedure requiring >1 reinflation
Ease of device placement	Multi-question form to be filled by anesthetist after intubation
Overall ease of intubation	Subjective score 0-10; where 0 – worst, 10-best
Laryngoscope insertion	--/--
Glottic view	--/--
DLT delivery	--/-- placement of DLT mouth → into glottis proximity
DLT placement	--/-- ease of placing DLT through glottic opening

Study design and methods

This is a prospective, randomized, three-armed trial to investigate the efficacy of a radically curved DLT stylet to facilitate GlideScope-assisted tracheal intubation (Group 1) as compared to the commercial standard of GlideScope with GlideRite stylet (Group 2) and a direct laryngoscopy with Macintosh blade and a regular DLT stylet (Group 3).

This study will not impart additional risks on the patient in excess of those routinely cited for placement of the double-lumen endobronchial tube. All of the modern intubation modalities will be available at the intubation time, arguably decreasing the risk of an ultimately failed securing of patient's airway.

Following informed consent, each subject will be identified via a unique alpha-numeric code and randomized to either of 3 initial DLT placement technique groups. In all cases, the other 2 intervention modalities will be available in the event of failed 1st attempt intubation and will be used at practitioner's discretion. Patient's medical history and detailed airway exam will be recorded on the study form, including Mallampatti score, thyromental distance, ability to prognathize the mandible, any limitation in neck flexion/extension, any evidence of poor dentition or pre-existing dental damage, patient's height, weight and BMI.

Patient will then be taken to the operating room and anesthesia will be induced in the standard fashion per provider's discretion after denitrogenation of patient with 100% O₂ until EtO₂ value is greater or equal to 80%.

Laryngoscopy with the specified randomization modality will be performed by the anesthetist or fellow with timing of intubation recorded as described above. DLT size used will be recorded on the form as well.

The placement of DLT will be verified in a standard fashion using fiberoptic bronchoscopy, auscultation and capnometry. The anesthetist/fellow then will complete their experience questionnaire portion of evaluation. After the conclusion of the procedure, patient will be extubated using standard ASA guidelines and taken to the Post-Operative Admission Unit (PACU), where the final evaluation of patient will take place, assessing voice change and throat pain as described above. This will conclude our study period and patient care will be resumed.

Human Selection Criteria

We plan to enroll up to 130 subjects in order to achieve 120 evaluable subjects with 40 in each arm at Emory University Hospital (EUH) and Emory University Hospital Midtown (EUHM). We will include patients that are scheduled for a thoracic surgical intervention in which surgeon requests lung isolation, including but not limited to: VATS, open thoracic surgery for lung or esophageal disorder, thoracic duct intervention, sympathectomy procedure.

Inclusion Criteria

- Male and female patients requiring DLT placement for their surgery at EUH or EUHM
- Patients willing and able to provide written informed consent

Exclusion Criteria

- Patients in whom a previously difficult airway manipulation was recorded on an anesthetic record.
- Lung transplantation procedures, as underlying pulmonary disorder will confound SpO₂ metric.
- Any patient who is receiving anticoagulants in excess of a daily aspirin, patients with INR >1.4
- Patients in whom one lung ventilation or placement of DLT is contraindicated.
- Patients who require a rapid-sequence intubation.
- Patients undergoing emergency procedures.

Patients who meet eligibility based upon the above criteria will initially be screened by the study team in concert with the patient care team. The study design will be explained to the patient and their interest assessed. Sufficient time will be allotted for the patient to discuss the study in detail with a study investigator, read the informed consent, ask any questions, and sign the informed consent prior to performing the study protocol. This will permit final confirmation that the patients who are enrolled in the study do not have airway anatomy consistent with an expected difficult airway and therefore meeting exclusion criteria for this study.

Estimated time to completion of study: 24 months from enrollment of first subject.

Statistical Analysis

The protocol in Russel's paper and previously cited data within their paper indicated that statistical significance can be attained at 30 subjects in each arm for 2 intervention comparison.

In our evaluation with 3 treatment arms, increasing sample size to 40 patients should provide adequate statistical power. Categorical data will be analyzed using Fisher's exact test. Mann-Whitney and Student's t-test will be applied where appropriate for continuous variables.

Adverse Event Reporting

The study team will comply with Emory University IRB policies for reporting adverse events. In this study, events that are determined by the Principal Investigator to be related to the research will be recorded and reported. Additionally, all deaths, related or unrelated, will be reported to the IRB. All events that are unanticipated problems that are related or possibly related to the research and place the subject or others at greater risk of harm than anticipated will be immediately reported to the Emory IRB.

Data and Safety Monitoring Plan

The data will be continuously analyzed to ensure there is not a significant trend that warrants early termination of the study. The PI will conduct monitoring after the first 10 patients are enrolled and again halfway through the study at 60 patients to evaluate for any related adverse events and ensure continued patient safety. Any serious complications encountered by the anesthesiologist in the room will be relayed to the principal investigator or co-investigators.

All investigators will complete the required training for conducting research at Emory University. All investigators will be made aware of the adverse event reporting policy and will report these events to the principal investigator in a timely manner.

References

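### Does the silence on how a failed first attempt is timed and attributed undermine the primary comparison of placement time?

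*Combined protocol and SAP*

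**What the plan says.** The protocol's Objectives section names the primary outcome: "The primary outcome measures will be the mean time it takes to place a DLT with each modality". First-attempt success is a separate secondary outcome.

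Table 1 has one timed metric, the duration of laryngoscopy. It begins "Time from laryngoscope at pt's lips through" and ends at the first detection of end-tidal CO₂. That this row is the primary outcome is an inference, but no other row is timed. Table 1 defines first-attempt success as "DLT placed during initial laryngoscopy, within 120s".

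Study design and methods says that patients are "randomized to either of 3 initial DLT placement technique groups" and that "the other 2 intervention modalities will be available in the event of failed 1st attempt intubation and will be used at practitioner's discretion". On timing it says: "Laryngoscopy with the specified randomization modality will be performed by the anesthetist or fellow with timing of intubation recorded as described above". The form also holds the airway examination, and "DLT size used will be recorded on the form as well".

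Human Selection Criteria gives the numbers: "We plan to enroll up to 130 subjects in order to achieve 120 evaluable subjects with 40 in each arm". The word evaluable is not defined. Statistical Analysis lists tests (Fisher's exact, Mann-Whitney, Student's t) and names no analysis set.

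**The concern.** A patient whose first attempt fails, and who is then intubated with another arm's device, has no completed time on the device to which they were randomised. If time with each modality means time on that device alone, an analyst could leave the patient out, restart the clock at the second attempt, or credit the time to the device that finished. Each choice hides some or all of the cost of failing.

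The techniques may well differ in how often they fail. The Introduction cites an earlier trial that favoured the Macintosh blade on intubation success, and suggests that the stylet may explain the GlideScope's difficulties. A comparison restricted to successes could then give a different answer from one that keeps every randomised patient. The number of attempts and the finishing device are not among the listed data items, so part of the handling could not be reconstructed later.

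**Working it through.** **The plan's own figures.** 3 × 40 = 120 evaluable. With 130 enrolled, the allowance for loss is 10/130 = 7.7%. These agree with each other. Neither figure says that failed attempts count as losses.

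**The wording, side by side.**

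- Table 1 has one start (lips) and one stop (first end-tidal CO₂). It has no stop for a failed attempt and no second start. Read literally, the clock runs until the tube delivers CO₂.
- Randomisation is to an initial technique. That word allows for a later technique and keeps the patient in the group in which they started.
- Timing is recorded by reference back to Table 1, so no second rule competes with it.
- Time with each modality is ordinary shorthand for time in each arm. It can be stretched to mean time on the device alone, but nothing else in the protocol supports that.

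**What departing from this reading would do.** The documents give no times or failure rates, so all inputs here are assumed: log-normal success times (log-SD 0.4, at most 120 s), 40 per arm, one pair of arms, and a two-sided 5% t-test. A failed first attempt lasts 60–120 s, the gap 30–90 s, and the rescue has a median of 45 s, so a rescued case averages R ≈ 198 s in total. Mean success times are 48.1 s (median 45) and 37.8 s (median 35).

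With failure rate p and mean success time m, an arm's running-clock mean is (1 − p)·m + p·R. With failures dropped it is m.

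Lead case, 45 s/5% against 35 s/15%:

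- Dropped: 37.8 − 48.1 = −10.3 s.
- Running: (0.85 × 37.8 + 0.15 × 198) − (0.95 × 48.1 + 0.05 × 198) = 61.8 − 55.6 = +6.2 s.
- By simulation, the second arm is declared faster in about 70% of trials if failures are dropped and about 60% if the clock restarts (−8.8 s). On the running clock (+6.3 s) it is declared slower in about 6%.

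Other assumed settings, second arm minus first:

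| Arm 1 | Arm 2 | Failures dropped | Running clock |
|---|---|---|---|
| 45 s, 5% | 35 s, 5% | −10.3 s | −9.8 s |
| 45 s, 5% | 35 s, 10% | −10.3 s | −1.8 s |
| 45 s, 5% | 35 s, 15% | −10.3 s | +6.3 s |
| 45 s, 5% | 45 s, 15% | 0.0 s | +14.9 s |
| 45 s, 15% | 35 s, 5% | about −10 s | about −25 s |

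The last row by formula: (0.95 × 37.8 + 0.05 × 198) − (0.85 × 48.1 + 0.15 × 198) = 45.8 − 70.6 = −24.8 s.

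Dropping failures therefore creates an advantage only when the faster device also fails more often. When the slower device fails more, it understates a real advantage. When failure rates are equal, it hardly moves the mean difference.

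**What can be checked afterwards.** Table 1 records duration and first-attempt success for each patient. Given those two, anyone can exclude failures or rank them last and compare the results. A restarted clock or credit to the finishing device could not be undone from the listed items. The form itself is not reproduced, and the list of history and airway items in Study design and methods is introduced as a partial one.

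**The case for a change.** The strongest case for a change is that the gap touches the primary outcome and that the trial's own rationale expects the techniques to differ in failure. Under the assumptions above, a 10 s advantage is cancelled at p₂ = (55.6 − 37.8)/(199 − 37.8) = 11.1% against 5% (R = 199 s; 9.6% to 13.7% for R from 250 down to 150 s). That is about 2.4 extra failures in 40. A few sentences and two form fields would remove the doubt.

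Part of this stands. No sentence states the clock, attribution or retention rule, evaluable is undefined, and the arithmetic reproduces. The rest is weaker. The rule one would write down is the one that Table 1 and the initial-technique randomisation already lead to, so writing it would record the expected analysis and not alter it. The claim that a failed case has no time on its own device is also too broad. A first attempt completed after 120 s fails the Table 1 success definition but has a full time on its own device, and so does a repeat attempt with the same device, which the protocol does not rule out.

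One could also ask for Mann-Whitney as the named test because the times are skewed. That is a trade-off, since the primary outcome is a mean. At 45 s/5% against 35 s/30% the second arm's mean is about 30 s longer. The t-test calls it slower in about 60% of trials and Mann-Whitney in about 4%. With 5% failure in both arms the order reverses: Mann-Whitney has 66% power for the 10 s difference and the t-test 25%.

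**Conclusion.** The omission is real but is a missing detail that analysts fill sensibly. One lips-to-CO₂ time per patient, analysed by randomised initial technique, is the natural reading of Table 1 and Study design and methods, and it gives a sound comparison. Nothing in the protocol drops failures, restarts the clock or reassigns patients. First-attempt success is reported as its own outcome, so the failures stay in view beside the times.

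If an analyst did depart from that reading, the shift in the lead case would be about 16 s (from −10 s to +6 s). It would be about 15 s in the opposite direction when the slower device fails more (−10 s against −25 s), and about half a second when failure rates are equal. All of these rest on assumed times and failure rates. The conclusion rests on the plain reading of Table 1 being the one applied. No change to the plan follows.

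### First-attempt endobronchial success is defined without any bronchial-position criterion, so a tube in the trachea or the wrong bronchus could be counted as a success

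*Combined protocol and SAP*

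**What the plan says.** Four places in the protocol bear on this.

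- **Objectives.** The primary outcome is a time: "The primary outcome measures will be the mean time it takes to place a DLT with each modality". The first secondary outcome is the "success rate of first endobronchial intubation attempt".
- **Table 1, outcome rows.** The first-attempt success row reads "DLT placed during initial laryngoscopy, within 120s". The Duration of laryngoscopy row, the only time metric in the table, reads "Time from laryngoscope at pt's lips through 1 st EtCO ₂ detection".
- **Table 1, ease scores.** The DLT placement item is the "ease of placing DLT through glottic opening".
- **Study design and methods.** The purpose of the curved stylet is "to facilitate GlideScope-assisted tracheal intubation". After the laryngoscopy and timing step, the text states: "The placement of DLT will be verified in a standard fashion using fiberoptic bronchoscopy, auscultation and capnometry". It does not say that the bronchoscopic finding is recorded as study data, timed, or used to decide any outcome.

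Table 1 has no row for tube position or malposition.

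**The concern.** The outcome named in the Objectives and the rule that scores it are not the same. The name promises entry into a bronchus. The rule asks only that the tube be placed during the first laryngoscopy within a time limit. EtCO2 detection, the end of the only clock, shows that the tube is in the airway and says nothing about which part of it.

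Patients are eligible because the surgeon wants lung isolation, so bronchial position is what the tube is for. The three arms differ in the curve given to the tube: Appendix A contrasts a U shape with the J of the commercial stylet, and the third arm uses a regular stylet. If curvature affected where the tip ends up, no listed outcome would show it. The trial could report equal first-attempt success, or a faster technique, while the arms differed in correct bronchial placement.

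**Working it through.** The point is one of definition, so the main check is to set the texts side by side.

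1. **Name against rule.** The Objectives say endobronchial. The Table 1 row drops that word and gives two conditions: the tube is placed at the initial laryngoscopy, and within 120 s. Neither concerns the bronchus.
2. **Meaning of placed.** No definition is given. The nearest use in Table 1, the ease score, means passage through the glottis, and the design statement speaks of tracheal intubation. Both point to airway entry.
3. **Order of events.** Success must occur during laryngoscopy. Bronchoscopic verification is described after the laryngoscopy and timing step. This makes it less likely that placed means bronchoscopically verified, but does not exclude it.
4. **The 120 s clock.** The success row does not say when the 120 s starts or stops. The lips-to-first-EtCO2 interval is the only clock in the plan, so it is the natural one, but that is an inference.
5. **Use of the verification.** Neither the success row, the time row nor any complication row refers to it.

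The plan states no figure for success or malposition, so there is nothing of its own to reproduce. The only document input to the illustration below is the denominator: "We plan to enroll up to 130 subjects in order to achieve 120 evaluable subjects with 40 in each arm". Every rate is assumed.

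Let S be the proportion recorded as first-attempt successes and m the share of those not in the intended bronchus.

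- Confirmed endobronchial success = S × (1 − m)
- Patients misclassified per arm = 40 × S × m

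With S = 95%:

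| m | Confirmed success | Misclassified of 40 |
|---|---|---|
| 5% | 0.95 × 0.95 = 90.25% | 1.9 |
| 10% | 0.95 × 0.90 = 85.5% | 3.8 |
| 20% | 0.95 × 0.80 = 76% | 7.6 |
| 30% | 0.95 × 0.70 = 66.5% | 11.4 |

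The effect on a comparison depends on whether m differs between arms. Take recorded success of 90% against 70%, 40 per arm, and a two-sided Fisher's exact test at 0.05 (the plan names the test but no significance level). Power on the recorded outcome is 53%.

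- **Equal m of 5%, 10%, 20% or 30%:** confirmed success is 85.5% v 66.5%, 81% v 63%, 72% v 56% or 63% v 49%. The difference shrinks from 20 points to 19, 18, 16 or 14, and power falls to 43%, 35%, 24% or 19%.
- **m of 30% in the better arm and 10% in the other:** 0.90 × 0.70 = 63% and 0.70 × 0.90 = 63%. The difference disappears.
- **m of 10% and 30%:** 0.90 × 0.90 = 81% and 0.70 × 0.70 = 49%. The difference widens to 32 points, with power 81%.

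So the recorded outcome could overstate, understate or hide a difference in endobronchial success. The documents do not allow a choice among these cases.

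**The case against.** The strongest reply is that this is a trial of laryngoscopy and tracheal entry, with one stray adjective in the Objectives. The Table 1 row label itself omits the word endobronchial, the design speaks of tracheal intubation, and the time row has an explicit start and stop. On that view, correcting the label is enough. This stands in part: relabeling would remove the inconsistency. It would still leave bronchial position out of a comparison of devices for placing a double-lumen tube, although the examination that shows it is already part of the procedure.

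A second reply is that placed could mean verified, since bronchoscopy is specified. That reading is possible, and it limits what can be claimed. A reader might infer that success, like the time metric, stops at EtCO2, or that malpositioned tubes will certainly be counted as successes. The documents support neither. The success row contains no EtCO2 criterion, and an undefined word makes miscounting possible, not certain. Nor can it be said that the bronchoscopic finding goes unrecorded, because the study form is not among the documents.

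Third, nothing in the documents shows that stylet shape affects bronchial position. That is correct. An effect is plausible but unproven, and the unequal-rate examples show only what the outcome could miss.

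Finally, the endpoints were adapted from a published trial, and a changed definition could cost comparability. Reporting the through-glottis result alongside largely answers this.

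**Conclusion.** The point holds as a gap in definition. The named secondary outcome is not tied to bronchial position, and two assessors could score the same wrong-bronchus tube differently without departing from the plan. The timed primary has a clear stop point and needs only an accurate description.

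The size is unknown. The range of about 2 to 11 misclassified patients per 40 rests entirely on an assumed 95% recorded success and an assumed 5% to 30% malposition. The conclusion itself does not depend on those rates. The matter does not invalidate the trial. It should be corrected because the correction is cheap and makes the outcome measure what its name says.

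**What to change.** - Record for every patient the intended side and the finding at the first bronchoscopic look (correct, wrong side, or tracheal), and add that finding to Table 1 as its own row.
- Define first-attempt endobronchial success as both (a) the tube passed during the initial laryngoscopy within 120 s on the lips-to-first-EtCO2 clock and (b) the bronchial lumen in the intended bronchus at that first look. A patient who fails (a) is a failure whatever a later look shows, since a later attempt may use another technique.
- Report condition (a) alone as first-attempt tracheal success.
- Describe the primary outcome as time from lips to first EtCO2.

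The cost is one or two fields on a form, completed around an examination that the protocol already specifies. Reported endobronchial success will be somewhat lower than under the present rule. If the sponsor wants only the tracheal outcome, renaming it is the minimum change, but bronchial placement would then remain uncompared.

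### The SpO₂ complication is a yes/no at 96% with no starting or lowest value, so it is an insensitive measure and could count patients who were already below 96%

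*Combined protocol and SAP*

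**What the plan says.** Table 1 of the combined protocol and SAP defines the metric in full as SpO₂ "<96% during intubation", answered yes or no. It names no starting value, lowest value, depth or duration, and gives no rule for a patient who is already below the threshold.

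The Objectives section does not name SpO₂. It falls under complication incidence: "Secondary outcome measures include success rate of first endobronchial intubation attempt; assessment of difficulty by the provider and complication incidence".

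Three other places bear on the point:

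- **Study design and methods.** Anesthesia is induced "after denitrogenation of patient with 100% O₂ until EtO₂ value is greater or equal to 80" percent. This target is an end-tidal oxygen concentration. No SpO₂ value is required before laryngoscopy. The same section says "Patient's medical history and detailed airway exam will be recorded on the study form" and lists the items; a starting SpO₂ is not among them.
- **Human Selection Criteria.** One exclusion reads "Lung transplantation procedures, as underlying pulmonary disorder will confound SpO₂ metric". Eligible procedures include "open thoracic surgery for lung or esophageal disorder".
- **Statistical Analysis.** Categorical data go to Fisher's exact test. No adjustment for a starting value is mentioned.

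**The concern.** There are two separate weaknesses.

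First, the definition does not tie the event to the intubation. Someone at 95% when the blade enters can be scored as a complication of the technique, although the technique cannot have caused it. Such events are expected equally in every arm, so they raise all the recorded rates and shrink the difference between them. The protocol itself regards lung disease as a threat to this metric in transplantation. Patients having surgery for other lung disorders remain eligible, and it is a reasonable inference that the same worry applies to some of them.

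Second, even if every patient starts at or above 96%, a yes/no at one threshold ignores how far saturation fell. SpO₂ is the only oxygenation measure in Table 1. If the techniques differ in depth of desaturation, the planned comparison is poorly placed to show it.

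**Working it through.** **The plan's own figure.** The documents give no expected rate, power or effect size for SpO₂, so there is nothing to reproduce for this outcome. The one input they supply is 40 evaluable patients per arm. The event rates and the share of low starters below are assumptions.

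**1. Dilution by low starters.** Let p be the true rate of new desaturation and b the share of patients below 96% at the start, all scored yes. Then

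recorded rate = b + (1 − b) × p,

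and the difference between two arms shrinks by the factor (1 − b). Take p = 5% v 25%. At b = 10% the recorded rates are 0.10 + 0.90 × 0.05 = 14.5% and 0.10 + 0.90 × 0.25 = 32.5%, a difference of 18 points instead of 20. Power is for the exact Fisher test, 40 per arm, two-sided 0.05, summed over all possible tables:

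| Share starting low (b) | Recorded rates | Difference (points) | Fisher power |
|---|---|---|---|
| 0% | 5.0% v 25.0% | 20.0 | 65% |
| 1% | 5.95% v 25.75% | 19.8 | 61% |
| 2% | 6.9% v 26.5% | 19.6 | 58% |
| 5% | 9.75% v 28.75% | 19.0 | 50% |
| 10% | 14.5% v 32.5% | 18.0 | 39% |
| 20% | 24.0% v 40.0% | 16.0 | 25% |

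Other assumed rates show the same pattern. For 10% v 40%, power is 85% at b = 0, 82% at 2% and 66% at 10%. For 10% v 30% it is 53%, 49% and 35%.

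**2. What leaving low starters out of the count recovers.** The rates return to 5% v 25%, but the arms are smaller. At b = 10%, 40 × 0.90 = 36 per arm remain and power is 57%, against 39% as written. At b = 20%, 32 per arm remain and power is 48%, against 25%. Neither reaches 65%.

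**3. The cost of the yes/no cut when b = 0.** For a normally distributed measure cut so that a share p are events, the information kept relative to the full measure is φ(z)² / [p(1 − p)], where z is the normal quantile at p:

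- p = 10%: 0.1755² / 0.09 = 0.34
- p = 20%: 0.2800² / 0.16 = 0.49
- p = 50%: 0.3989² / 0.25 = 0.64

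**4. Does a ceiling at 100% undo this?** After preoxygenation many lowest values may tie at the top. In a simulation of 5% v 25% at 40 per arm, with 30% to 70% of the lower-risk arm at the 100% ceiling, a rank test on the lowest value had 96% to 99% power, against about 64% to 66% for the yes/no count. This assumes that the technique shifts the whole distribution of lowest values. The gain would be smaller if it affected only a few patients.

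**The case against.** The strongest objection is that low starters may hardly exist. Every patient breathes 100% oxygen to the end-tidal target before induction, and emergency and rapid-sequence cases are excluded. If the share is 1% or 2%, the 5% v 25% scenario loses only about 3 to 6 points of power. This stands as far as it goes: the documents show that such patients could be counted, not that they will be. They also set no SpO₂ condition before laryngoscopy, and Table 1 captures nothing from which the share could be learned.

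A reader might infer that the protocol itself says lung disease confounds this outcome in the enrolled patients. It does not. The words "as underlying pulmonary disorder will confound" give the reason for excluding lung transplantation, and extending them to other lung disorders is an inference.

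A reader might also infer bias between the arms. Randomisation rules that out in expectation and leaves lost sensitivity and chance imbalance.

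The power figures depend on assumed rates. With 5% v 15%, Fisher power is only 18% at b = 0 and 12% at b = 10%, so the count would tell little either way. The study form is not in the documents and might capture a lowest value, but no planned metric uses one.

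None of this answers the second weakness, which needs no low starters.

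**Conclusion.** The point holds as a modest measurement weakness. As worded, Table 1 could score a patient already below 96% as an event, and it treats a trivial fall and a deep one alike.

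The dilution depends entirely on an unknown share. Under assumed rates of 5% v 25% it is a few points of power if that share is 1% to 2%, and 26 points (65% to 39%) if it is 10%. The loss from the yes/no cut is the firmer part, because it applies whatever the share. The 34% to 64% range rests on a roughly normal measure, which SpO₂ is not, so it should be read as indicative.

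The effect is confined to one component of a secondary outcome. The primary comparison of placement time is untouched, and nothing here calls for a change to the 40 per arm.

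**What to change.** Record two numbers: SpO₂ when the laryngoscope reaches the lips, and the lowest SpO₂ until first EtCO₂ detection. Table 1 already uses both time points for duration of laryngoscopy.

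Compare the lowest value between arms by ranks in all patients, accounting for the starting value. Keep the below-96% yes/no as a descriptive count, and report patients who start below 96% separately. Using all patients in the main SpO₂ comparison matters: a patient who starts at 95% and falls to 70% would drop out of a restricted count but stays in this one.

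The cost is two more form entries from a monitor already in use, a slightly smaller denominator for the yes/no count, and possible ties near 100% in the rank analysis. Sample size and patient care do not change.
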